2. Dependent Variables: Injury report according to DMSS or self-reported

3. Determine if general self-efficacy is a predictor of performance during CBT by performing a multivariate regression between a single self-efficacy assessment and multiple measures of performance during CBT including 1) successful completion (pass/fail), 2) Army Combat Fitness Test (ACFT) raw or calculated score, 3) Warrior Competition performance, 4) marksmanship score, 5) written exams, 6) swimming assessment and 7) any other individually graded events.

1. Independent Variable: Cadet General Self-Efficacy score

2. Dependent Variables: performance outcome by event- 1) successful completion (pass/fail), 2) Army Combat Fitness Test (ACFT) score, 3) Warrior Competition performance, 4) marksmanship score, 5) written exams, 6) swimming assessment and 7) any other individually graded events.

4. Determine if task-specific self-efficacy is a predictor of performance during CBT by performing a multivariate regression between a single (or multiple) assessments of cadet task-specific self-efficacy, and multiple measures of performance during CBT including 1) successful completion (pass/fail), 2) Army Combat Fitness Test (ACFT) raw or calculated score, 3) Warrior Competition performance, 4) marksmanship score, 5) written exams, 6) swimming assessment and 7) any other individually graded events.

1. Independent Variable: task-specific self-efficacy scores

2. Dependent Variables: performance outcome by event including 1) successful completion (pass/fail), 2) basic rifle marksmanship qualification score, 3) 12-mile road march outcome (pass/fail), 4) Army Combat Fitness Test (ACFT) score, 5) land navigation score, 6) swimming assessment outcome (pass/fail) and 7) any other individually-graded events.

5. After completing CBT, determine which sources of self-efficacy ((1) enacting mastery experiences, 2) vicarious experiences, 3) verbal persuasion, 4) physiological state, 5) affective state, 6) mental imagery) were the most influential on cadets' self-efficacy throughout CBT specific tasks by conducting a Chi-square test.

1. Independent Variable: reported level of influence of each (6) source of self-efficacy.

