2. Dependent Variables: performance outcome by event including 1) successful completion (pass/fail), 2) basic rifle marksmanship qualification score, 3) 12-mile road march outcome (pass/fail), 4) Army Combat Fitness Test (ACFT) score, 5) land navigation score, 6) swimming assessment outcome (pass/fail) and 7) any other individually-graded events.

6. Determine the effect of low back pain education (cautionary vs resiliency) on deadlift performance (weight lifted).

We will analyze this with MDL weight lifted as the dependent variable (one-way ANOVA), with a planned comparison analysis if significant differences are found between groups.

7. Determine the degree of confidence cadets have in their ability to succeed at the MDL both before and after the education and MDL

We will analyze if there is a main effect of time in the pre-to-post self-efficacy scores with a paired t-test. We will use multiple regressions to analyze the impact of self-efficacy scores on MDL performance.

8. Determine the effect of low back pain education (cautionary vs resiliency) on deadlift self-efficacy. We will analyze change scores with one-way ANOVA with planned comparisons between groups if ANOVA is significant.

9. Determine the effect of low back pain education (cautionary vs resiliency) on perceived spine vulnerability on a deadlift.

We will analyze change scores with one-way ANOVA with planned comparisons between groups if ANOVA is significant.

9.4 Study Design:

Describe study design in one to two sentences (e.g., prospective, use of existing records/data /specimens, observational, cross-sectional, interventional, randomized, placebo-controlled, cohort, etc.). Specify the phase - Phase I, II, III, or IV- for FDA-regulated investigational drug research

This study will be a randomized controlled trial with parallel design and 1:1 allocation ratio. We plan to use cluster randomization. We will have three groups- control, cautionary, resiliency (Jackson, 2005).

9.5 Target Population:

Describe the population to whom the study findings will be generalized

U.S. Military Academy Cadets

9.6 Benefit to the DoD:

State how this study will impact or be of benefit to the Department of Defense

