Cadet Demographics: Age, gender, height, weight, USMA Preparatory School attendance, intended athletics participation, intended USMA performance

Injury Questionnaire: Recent injury information (within last year), still effecting performance, and Single Assessment Numeric Evaluation (SANE), and after-cadet basic training injury presence, region, and limiting classification

Self-Efficacy: Overall Cadet Basic Training performance, marksmanship, buddy team live fire, swimming 150 yards, ruck marching (load carriage), ACFT, deadlift, land navigation

Maximum Deadlift (MDL) performance: Measured by the amount of weight successfully lifted during the ACFT.

Reported Self-Efficacy Source: Measured on the post-CBT survey using Qualtrics. The cadets will rank-order commonly cited sources of self-efficacy from most to least influential. The options will include commonly-cited self-efficacy sources: physiological state, previous experiences, affective state, mental imagery, vicarious experiences, and verbal persuasion.

10.3 At any point in the study, will you request, use, or access health information in any form, including

verbal, hard copy and electronic?

Yes No

10.4 Review the definitions below and respond to the following two questions. If you are not sure of the answers, email [contact] for assistance. The Military Health System (MHS) is defined as all DoD health plans and DoD health care providers that are organized under the management authority of, or in the case of covered individual providers, assigned to or employed by, the Defense Health Agency (DHA), the Army, the Navy, or the Air Force. MHS workforce members are employees, volunteers, trainees, and other persons whose conduct, in the performance of work for the MHS, is under the direct control of the MHS, whether or not they are paid by the MHS. MHS business associates are persons or entities that provide a service to the MHS and require protected health information (PHI) to provide the service.

Are you an MHS workforce member?

Yes, I am an MHS workforce member
 No, I am not an MHS workforce member

Are you an MHS business associate?

Yes, I am an MHS business associate
 No, I am not an MHS business associate

10.5 Have you consulted with an MHS data expert to determine the data elements required for your study?

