4. Determine if task-specific self-efficacy is a predictor of performance during CBT by performing a multivariate regression between a single (or multiple) assessments of cadet task-specific self-efficacy, and multiple

measures of performance during CBT including 1) successful completion (pass/fail), 2) Army Combat Fitness Test (ACFT) raw or calculated score, 3) Warrior Competition performance, 4) marksmanship score, 5) written exams, 6) swimming assessment and 7) any other individually graded events.

1. Independent Variable: task-specific self-efficacy scores by event
2. Dependent Variables: performance outcome by event- 1) successful completion (pass/fail), 2) Army Combat Fitness Test (ACFT) score, 3) Warrior Competition performance, 4) marksmanship score, 5) written exams, 6) swimming assessment and 7) any other individually graded events.

5. After completing CBT, determine which sources of self-efficacy (1) enacting mastery experiences, 2) vicarious experiences, 3) verbal persuasion, 4) physiological state, 5) affective state, 6) mental imagery) were the most influential on cadets' self-efficacy throughout CBT specific tasks including 1) successful completion (pass/fail), 2) Army Combat Fitness Test (ACFT) raw or calculated score, 3) Warrior Competition performance, 4) marksmanship score, 5) written exams, 6) swimming assessment and 7) any other individually graded events by conducting a Chi-square test.

1. Independent Variable: task-specific events 1) successful completion (pass/fail), 2) Army Combat Fitness Test (ACFT) score, 3) Warrior Competition performance, 4) marksmanship score, 5) written exams, 6) swimming assessment and 7) any other individually graded events.
2. Dependent Variables: reported level of influence of each (6) source of self-efficacy.

6. Determine the effect of low back pain education (cautionary vs resiliency) on deadlift performance (weight lifted).

We will analyze this with MDL weight lifted as the dependent variable (one-way ANOVA), with a planned comparison analysis if significant differences are found between groups.

7. Determine the degree of confidence cadets have in their ability to succeed at the MDL both before and after the education and MDL

We will analyze if there is a main effect of time in the pre-to-post self-efficacy scores with a paired t-test. We will use multiple regressions to analyze the impact of self-efficacy scores on MDL performance.

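### Objective 5 applies an ordinary Chi-square test to rankings of six sources by the same cadets, with no table defined and predictor and outcome reversed between 9.3 and 11.6; the error rate can go either way

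*Combined protocol and SAP*

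**What the plan says.** Section 10.2 (Data Collection) describes the measurement: "The cadets will rank-order commonly cited sources of self-efficacy from most to least influential". The six options are "physiological state, previous experiences, affective state, mental imagery, vicarious experiences, and verbal persuasion". Section 10.1, Phase 5, links these questions to task-specific events. Neither section says whether a cadet gives one ranking overall or one per event.

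Objective 5 asks which sources were most influential. Its entry in section 11.6 ends "any other individually graded events by conducting a Chi-square test". The variable roles differ between the two places where the objective appears:

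- Section 9.3: "Independent Variable: reported level of influence of each (6) source of self-efficacy", with "Dependent Variables: performance outcome by event including 1) successful completion (pass/fail), 2) basic rifle marksmanship qualification score" and further events.
- Section 11.6: "Independent Variable: task-specific events 1) successful completion (pass/fail), 2) Army Combat Fitness Test (ACFT) score, 3) Warrior Competition performance" and further events, with "Dependent Variables: reported level of influence of each (6) source of self-efficacy".

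The event lists differ too. Section 9.3 has the road march and land navigation, where section 11.6 has the Warrior Competition and written exams. Section 11.1 names methods only for the back-education objectives, so nothing there defines the table for Objective 5. No significance level is stated.

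**The concern.** Pearson's Chi-square treats each count as an independent observation. A cadet who ranks six sources contributes six linked entries: giving one source rank 1 bars the other five from it. A cadet who answers for several tasks contributes several correlated answers. Either way, the usual reference distribution can be wrong.

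The reversed roles are a separate problem, because they describe two different analyses. Section 11.6 asks whether source influence varies by event. Section 9.3 asks whether source influence predicts performance, and several of its outcomes (marksmanship, ACFT, land navigation) are scores that cannot enter a Chi-square table until they are cut into categories. None are defined.

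What is at stake is the answer to Objective 5. Depending on the table, the test could report differences between sources that do not exist, or miss real differences between tasks. Leaving the table open also lets the choice be made after the data are seen.

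**Working it through.** **Inputs from the documents.** There are k = 6 sources, fully ranked (10.2). The test is an unqualified Chi-square (9.3, 11.6). For the number of cadets, 11.5 gives 969 evaluable and 1200 recruited.

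**Assumptions not in the documents.** Nominal level 5%; seven events; within-cadet correlation of latent preferences of 0, 0.2, 0.5 or 0.8; a 90% pass rate for the pass/fail layout. Clustering by company is ignored.

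**Plan's own figure.** None is given for Objective 5. The 969 belongs to the three-group deadlift ANOVA. It reproduces with f = 0.10, power 0.80 and an assumed level of 5%: total N = 966.5, and 966.5/3 = 322.2, rounded up to 323 per group, so 3 × 323 = 969. Here it serves only as a realistic n, and 500 and 1200 were also run.

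**Step 1: source-by-rank table, one ranking per cadet.** If all orders are equally likely, every cell has expectation n/k, and the centred counts have covariance n/(k−1) times the product of the row-centring and column-centring matrices. Dividing the squared deviations by n/k gives

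X² ~ [k/(k−1)] × χ² with (k−1)² df = (6/5) × χ² with 25 df.

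The nominal critical value is 37.65, so the true rejection rate is P(χ²₂₅ > 37.65 × 5/6) = P(χ²₂₅ > 31.375) = 0.177. Collapsing ranks to top three or not leaves 5 df and the same factor: P(χ²₅ > 11.07 × 5/6) = P(χ²₅ > 9.225) = 0.100. Neither result depends on n, so a larger sample does not help.

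**Step 2: simulation under no true difference, one ranking per cadet** (4,000 runs at each n; Monte Carlo standard error near 5% is √(0.05 × 0.95/4000) = 0.3 points).

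| Analysis | Rejection rate, n = 500 to 1200 |
|---|---|
| Source by rank, ordinary Chi-square | 17.3% to 18.6% |
| Same statistic × 5/6 | 4.7% to 5.4% |
| Source by top three or not | 10.0% to 11.0% |
| First choice only, goodness of fit | 4.5% to 5.4% |
| Friedman test | 4.8% to 5.8% |

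**Step 3: the same 969 cadets answering for seven events** (1,000 runs; standard error near 5% is 0.7 points; sources equally preferred).

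| Table, ordinary Chi-square | corr. 0 | 0.2 | 0.5 | 0.8 |
|---|---|---|---|---|
| Source by rank, pooled over events | 18% | 42% | 78% | 99% |
| First choices, pooled over events | 4% | 19% | 49% | 75% |
| Event by top source | 4.7% | 1.1% | 0.1% | 0% |
| Event by rank of one source | 4.4% | 3.4% | 0.9% | 0.1% |

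With unequal source preferences that are the same in every event, event by top source gives 4.0%, 2.2%, 0.1% and 0%. One source's rank against pass/fail within one event gives 4.4% to 6.2% over all scenarios.

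**Step 4: why the direction changes.** Pooling counts one cadet's repeated preference as several independent votes, so differences between sources look too certain. As a rough check on pooled first choices, let ρ be the correlation between one cadet's choices and m the number of tasks. The statistic is then inflated by 1 + (m−1)ρ. For m = 5 and ρ = 0.1 the rate is P(χ²₅ > 11.07/1.4) = 16%; for m = 7 and ρ = 0.5 it is P(χ²₅ > 11.07/4) = 74%. In an event-by-source table the comparison is between rows that hold the same cadets. Their shared preferences cancel, the rows differ less than independent samples would, and the test rejects too rarely.

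**The case against.** The strongest reply is that 17.7% belongs to a table the plan never names. A reader might infer that the false-positive rate for Objective 5 is well above 5%. The documents do not support that as a flat statement, because rows, columns and unit of count are all undefined. Under the roles in section 11.6 (events as predictor, source influence as outcome), a natural table is event by source. If the same cadets answer for every event, that test is conservative, and the harm is lost power. One first choice per cadet fits the question of which source is most influential and is valid, as is one source's rank against pass/fail within one event. The pooled figures also rest on correlations, and on a pooling step, that appear nowhere in the plan.

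All of that stands. It limits what can be said about the direction of error but does not rescue the plan. The measurement is a full ranking, and the variable is the influence of each of six sources, so a first-choice count is not what is written. The tables that hold about 5% are particular choices that the plan does not make. The reversal of predictor and outcome needs no calculation and is unaffected by this reply.

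It is also fair to say that a Friedman test per task compares sources within a task and does not test events as a predictor. A separate method is needed if that question is kept.

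**Conclusion.** The point holds as one of an undefined test on dependent data, plus a contradiction between sections 9.3 and 11.6. It does not hold as a demonstrated excess of false positives. At an assumed 5% level, the ordinary Chi-square rejects about 18% of the time for a source-by-rank table from one ranking per cadet. Pooling correlated rankings or first choices over tasks gives higher rates (42% and 19% respectively at an assumed correlation of 0.2). An event-by-top-source table with the same cadets in each row gives about 2% or less at 0.2 and near 0% at 0.5. The rate is about 5% if one first choice per cadet is counted, or one source's rank is set against pass/fail in one event.

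The 18% needs only the 5% level, a null in which all orders are equally likely, and that table. The repeated-task figures also need the assumed seven events and correlations. The effect is confined to Objective 5. It is worth correcting before analysis, but it does not touch the randomised deadlift comparison.

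**What to change.** In sections 9.3 and 11.6:

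1. Make source influence the outcome in both, with one list of events. If the link from source to performance is also wanted, state it as a separate analysis with a method suited to each outcome.
2. Say whether each cadet ranks once or once per task, and state the significance level.
3. For which source is most influential, replace the Chi-square with a Friedman test on each cadet's six ranks, separately per task if ranked per task. Follow it with Holm-adjusted paired comparisons, and report mean ranks with confidence intervals. If a Chi-square on the source-by-rank table is kept, use one ranking per cadet, multiply the statistic by 5/6 and refer it to 25 df.
4. If differences between tasks are tested, use a method that allows for repeated answers from one cadet, for example a model with a cadet random effect or cadet-clustered standard errors.

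The cost is wording only: the same survey data and standard software serve, and no sample size changes.

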Performance effects resulting from the messages provided to athletes shouldn't be ignored, and this is referred to as placebo (has a perceived positive effect) or nocebo (has a perceived negative effect (Horvath, 2021). The concept of performance decline after negatively-perceived stimulus has a less robust presence in the literature than placebo effects, though this is evolving. Numerous recent studies have now documented the significant detriments to physical performance when subjects are exposed to negative or potentially threatening information (Cook, 2012; Corsi, 2019; Emadi Andani, 2015; Horcajo, 2019; Jackson, 2005; Pollo, 2012; Zech, 2019).

To our knowledge, there are no longitudinal studies evaluating the risk of injury from deadlifting with a flexed lumbar spine resulting in no clear evidence that a flexed spine is a risk factor for injury. However, it is well documented that information related to potential threat (nocebo) can adversely affect physical performance. Our research aim is to determine if cautionary information about the risk of spine injury harms performance on a maximum strength test compared to a message of spine resiliency. The cautionary education is similar to standard information provided to many servicemembers before the start of an ACFT or a maximum deadlift.

9.3

Objectives/Specific Aims/Research Questions:

Describe the purpose and objective(s) of the study, specific aims, and/or research questions /hypotheses

1. Determine if general self-efficacy is a predictor of injury during Cadet Basic Training(CBT) by performing a Kaplan-Meier Survival Curve of a single self-efficacy assessment (Cadet General Self-Efficacy Assessment) and injury occurrence using the Defense Medical Surveillance System (DMSS), Cadet Illness and Injury Tracking System (CIITS), Armed Forces Health Longitudinal Technology Application (AHLTA) and a follow-up self-reported injury assessment.

1. Independent Variable: Cadet General Self-Efficacy score

2. Dependent Variables: Injury report according to CIITS, AHLTA, DMSS, sick call report or self-reported

2. Determine if task-specific self-efficacy is a predictor of injury during specific CBT events by performing a Kaplan-Meier Survival Curve, a single assessment of cadet task-specific self-efficacy and injury occurrence using DMSS, CIITS, AHLTA and a follow-up self-reported injury assessment.

1. Independent Variable: Cadet Task-Specific Self-Efficacy score

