11.0 Statistical/Data Analysis Plan

11.1 Statistical Considerations:

List the statistical methods to be used to address the primary and secondary objectives, specific aims, and/or research hypotheses. Explain how missing data and outliers will be handled in the analysis. The analysis plan should be consistent with the study objectives. Include any sub-group analyses (e.g., gender or age group). Specify statistical methods and variables for each analysis. Describe how confounding variables will be controlled in the data analysis

To determine the effect of low back pain education (cautionary vs resiliency) on deadlift performance (weight lifted), we will use ANOVA and planned comparison analysis if between-group differences are found between groups.

To determine the effect of low back pain education on deadlift self-efficacy, we will analyze change scores with a one-way ANOVA and planned comparisons if significant.

To determine the effect of low back pain education on perceived spine vulnerability, we will analyze change scores with a one-way ANOVA and planned comparisons if significant.

Our study design accounts for some confounding factors by utilizing randomization. Potentially confounding variables should be balanced between groups. We will test groups at baseline to ensure they are similar among important characteristics. Furthermore, characteristics that are different among groups at baseline or that appear to be influential on load lifted will be included in the ANOVA model as a covariate to control for and test for potential confounding.

11.2 Sample Size:

1200 participants

11.3 Total number of subjects requested (including records and specimens):

1200

11.4 If you are recruiting by study arm, please identify the arms of the study and how many subjects will be enrolled in each arm

N/A

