11.5 Please provide a justification for your sample size

We have powered this study to determine a between-group difference of 5kg. This is equivalent to an effect size of $d=.10$ given a standard deviation of 23kg (available from previously collected data in this lab). We used G*Power 3.0 with power at .80 to calculate a total sample size of 969 subjects (323 per group). We will therefore attempt to recruit 1200 participants, allowing for 20% injury or attrition which might prevent subjects from completing the MDL event during CBT ACFT.

11.6 Data Analysis Plan: Complete description: Background, Objectives, Design, Step by Step how the project is going to be done, Data analysis plan:

1. Determine if general self-efficacy is a predictor of injury during CBT by performing a Kaplan-Meier Survival Curve, a single assessment (Cadet General Self-Efficacy Assessment), analysis of the Defense Medical Surveillance System (DMSS) and a follow-up self-reported injury assessment.
 1. Independent Variable: Cadet General Self-Efficacy score
 2. Dependent Variables: Injury report according to DMSS or self-reported
2. Determine if task-specific self-efficacy is a predictor of injury during specific CBT events by performing a Kaplan-Meier Survival Curve, a single (or multiple) assessments of cadet task-specific self-efficacy, analysis of the Defense Medical Surveillance System (DMSS) and a follow-up self-reported injury assessment.
 1. Independent Variable: Cadet Task-Specific Self-Efficacy score
 2. Dependent Variables: Injury report according to DMSS or self-reported
3. Determine if general self-efficacy is a predictor of performance during CBT by performing a multivariate regression between a single assessment (Cadet General Self-Efficacy Assessment) and multiple measures of performance during CBT including 1) successful completion (pass/fail), 2) Army Combat Fitness Test (ACFT) raw or calculated score, 3) Warrior Competition performance, 4) marksmanship score, 5) written exams, 6) swimming assessment and 7) any other individually graded events.
 1. Independent Variable: Cadet General Self-Efficacy score
 2. Dependent Variables: performance outcome by event- 1) successful completion (pass/fail), 2) Army Combat Fitness Test (ACFT) score, 3) Warrior Competition performance, 4) marksmanship score, 5) written exams, 6) swimming assessment and 7) any other individually graded events.

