8. Determine the effect of low back pain education (cautionary vs resiliency) on deadlift self-efficacy.

We will analyze change scores with one-way ANOVA with planned comparisons between groups if ANOVA is significant.

9. Determine the effect of low back pain education (cautionary vs resiliency) on perceived spine vulnerability on a deadlift.

We will analyze change scores with one-way ANOVA with planned comparisons between groups if ANOVA is significant.

12.0

Participant Information

12.1 Subject Population:

All incoming US Military Academy cadets, class of '26, attending cadet basic training in the summer of 2022

12.2 AgeRange:

Check all the boxes that apply. If the age range of potential subjects (specimens, records) does not match the range(s) selected, please specify in the text box.

0-17

18-24

25-34

35-44

45-54

55-64

65-74

75+

12.3 Gender:

Male
Female
Other

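### The objectives name one pair, cautionary versus resiliency, but the plan tests it only after a significant three-group ANOVA; at the design inputs this costs about 4.5 to 11 points of power unless control lies outside the pair

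*Combined protocol and SAP*

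**What the plan says.** The design in 9.4 has three arms: "We will have three groups- control, cautionary, resiliency". The research aim at the end of 9.2 concerns two of them. It asks whether cautionary information "harms performance on a maximum strength test compared to a message of spine resiliency". Objective 6 names the same two: "Determine the effect of low back pain education (cautionary vs resiliency) on deadlift performance (weight lifted"). Objectives 8 and 9 repeat the pair for deadlift self-efficacy and perceived spine vulnerability.

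The analysis is gated wherever it appears:
- 9.3 and 11.6, Objective 6: one-way ANOVA on weight lifted, "with a planned comparison analysis if significant differences are found between groups".
- 9.3 and 11.6, Objectives 8 and 9: "We will analyze change scores with one-way ANOVA with planned comparisons between groups if ANOVA is significant".
- 11.1, deadlift performance: "we will use ANOVA and planned comparison analysis if between-group differences are found between groups".

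The planned comparisons are never listed. No significance level and no multiplicity rule are given, and no section tests cautionary against resiliency outside the gate.

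On sample size, 11.5 states: "We have powered this study to determine a between-group difference of 5kg". It continues: "This is equivalent to an effect size of $d=.10$ given a standard deviation of 23kg". With power 0.80 it arrives at 969 cadets, 323 per group.

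**The concern.** The F test asks whether any of three arms differ. The objectives ask whether two particular arms differ. A contrast chosen in advance needs no prior omnibus test: tested alone at 5%, its error rate is already 5%. Requiring the F test first adds a condition that depends on where the no-education arm falls, which has no bearing on the difference between the two messages. When control lies between the messages, the spread across three arms is diluted, and a real 5 kg difference may never be formally tested.

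The stated power is also affected. If 0.80 belongs to the F test, a reader of 11.5 does not know the chance that the trial will demonstrate the difference named in its objectives.

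**Working it through.** **Inputs.** From 11.5: difference 5 kg, SD 23 kg, 323 per group, total 969, power 0.80, effect size 0.10. From 9.4: three arms, equal allocation. Assumed, because not stated: 5% for the F test and two-sided 5% for the contrast. As in 11.5, cadets are treated as independent.

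**1. Reproducing 969.** For a one-way ANOVA with three groups, the noncentrality is N × f². With f = 0.10 and N = 969 it is 969 × 0.01 = 9.69, on 2 and 966 degrees of freedom, and power is 0.801. With 322 per group power is 0.7998, so 323 is the smallest size that reaches 0.80. The figure matches exactly as an omnibus F test at f = 0.10. It does not match as a two-group calculation: d = 0.10 would need 1,570 per group, and 5 kg with SD 23 kg would need 333. The 0.10 is labelled d, but 5/23 = 0.217, so it works only as Cohen's f.

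**2. The named pair tested directly.** The standard error of the difference is 23 × √(2/323) = 1.81 kg, and 5/1.81 = 2.76. Power is about Φ(2.76 − 1.96) = Φ(0.80) = 0.79. The t-based value is 0.788.

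**3. Power of the gate.** f is the standard deviation of the three true means divided by 23.
- Control midway (−2.5, 0, +2.5): √(12.5/3) = 2.041; f = 2.041/23 = 0.0887; noncentrality 7.63; F-test power 0.694.
- Control equal to one education arm (means −5, 0, 0): √(16.67/3) = 2.357; f = 2.357/23 = 0.1025; noncentrality 10.18; F-test power 0.821.

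**4. Both steps together.** The chance that the F test and the contrast are both significant, from 2,000,000 simulated trials per row:

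| Position of control | F test | Pair tested directly | F test and pair | Loss (points) |
|---|---|---|---|---|
| Midway | 0.694 | 0.788 | 0.681 | 10.7 |
| A quarter of the way | 0.731 | 0.788 | 0.702 | 8.7 |
| Equal to one education arm | 0.821 | 0.788 | 0.743 | 4.5 |
| Outside the pair by half the difference | 0.973 | 0.788 | 0.785 | 0.3 |

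**5. Sensitivity, control midway.** At 320 per arm (1,200 less 20%, divided by three) power is 0.677 gated and 0.784 direct, a loss of 10.7 points. At 400 per arm it is 0.782 and 0.867, a loss of 8.5. For a 4 kg difference at 323 per arm it is about 0.471 and 0.598, a loss of about 12.6.

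**6. Error rate without the gate.** With the two messages equal and control 5 kg away, the direct test rejected in 5.0% of simulated trials. The gate is not needed to hold the error of this one contrast.

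**The case against.** **The gate has a purpose.** With three groups, a significant F test before unadjusted pairwise tests does control error across the three pairs. If all three pairs matter equally, replacing the gate with Bonferroni would give about 0.64 for this pair, below the gated 0.68. This stands. The gain comes only from naming one contrast as primary and making the two with control secondary. That sets a priority among comparisons, and the study team has to agree to it. The aim and Objectives 6, 8 and 9 support the choice, but control is a full arm, and 11.1 does not repeat the pair for self-efficacy or spine vulnerability.

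**The sample size agrees with the first planned test.** 11.5 sizes an F test and the plan runs one. It never says that 0.80 is the power for cautionary versus resiliency. That also stands: the calculation is coherent, but it answers a different question from the one the objectives pose.

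**A reader might infer that the study expects control in the middle, so that 11 points is the loss to expect.** The documents do not support this. Section 9.2 describes both placebo and nocebo effects, which makes a midway control plausible. It also calls the cautionary message similar to standard information, which fits a control near that arm. The plan's 0.10 is closer to the one-arm pattern (0.1025) than to the midway pattern (0.0887), although 11.5 states no pattern. Nor is 11 points an upper bound, since the loss is larger at 4 kg.

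**Other features change the size.** Section 11.1 allows covariates. If they explained 30% of the variance (an assumption), the SD would be 23 × √0.70 = 19.2 kg and the losses would fall to about 6.8 points (midway) and 1.9 points (one arm). Whole companies are randomized, and this lowers both powers. With an assumed design effect of 4, direct power would be about 0.28 and gated power about 0.19 with control midway. Clustering is the larger problem, and removing the gate does not solve it.

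**Conclusion.** The concern holds as a mismatch between the pair the objectives name and the gated test, with a modest and avoidable loss of power. For Objective 6 at the plan's own inputs, the loss is about 4.5 points if control equals one education arm and about 11 points if it lies midway, and negligible if control lies outside the pair. The stated 0.80 is the power of the F test at f = 0.10, not of the two-step test of the named pair. These figures rest on an assumed two-sided 5% level and on ignoring clustering; the documents give neither the number of companies nor an intraclass correlation from which to correct them.

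For Objectives 8 and 9 only the rule carries over, because no SD or target difference is given. The gated approach is not invalid: it controls error across the three pairs. It is simply not the most direct or most powerful test of the question asked.

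**What to change.** In 9.3, 11.1 and 11.6, name cautionary versus resiliency as the primary contrast for Objectives 6, 8 and 9. Test it directly at two-sided 5%, without the omnibus condition, from a model that accounts for randomization by company. Make the two contrasts with control secondary, with Holm adjustment, and report all three differences with confidence intervals whatever the F test shows. In 11.5, state the significance level, correct the effect-size label, and restate the power for the primary contrast: about 0.79 at 323 per arm before allowing for clustering, which lowers it.

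The cost is a change of wording in four sections, with no extra cadets or data. The real concession is that the comparisons with control become secondary.
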